
To test our hypotheses, we propose to conduct a pilot randomized clinical trial with the following specific aims:

**Specific Aim 1:** To compare the effectiveness and adherence to 6 months of a novel Multi Modal Balance Intervention (MMBI) program versus Tai Chi exercise training to improving balance [Four-Square Step Test (FSST) and Functional Gait Assessment Tests (FGA)], gait (spatio-temporal gait parameters), lower extremity isometric strength (Biodex) and mobility fitness (distance covered during a 6 minute walk) pre and post intervention in older veterans at increased risk for falling.

H1: MMBI will result in larger improvements than Tai Chi in balance, gait, lower extremity strength, and mobility fitness.

H2: MMBI will have a higher adherence rate than a Tai Chi exercise program

[figure not shown]
**Specific Aim 2 (exploratory):** To determine and compare the effectiveness of 6 months of MMBI versus Tai Chi exercise training to prevent falls and reduce the number of serious falls in older veterans at increased risk for falling.

H1: MMBI will result in greater decreases in serious falls than Tai Chi and this will be maintained for 6 months following the completion of the exercise program.

Background and Significance:

Falls are complex and multi-factorial in origin with numerous deficits including impaired balance, decreased postural control, muscle weakness, sensory changes, and a composite inability to successfully negotiate environmental hazards and obstacles (see conceptual model). The majority of falls occur during walking, with incident slips and trips, such that targeted interventions focused on stepping and walking ability may be more effective at improving dynamic balance and reducing falls. Older adults are particularly vulnerable to falls during lateral or diagonal movements. While the mechanism of lateral instability remains under investigation, it is reasonable to suspect deterioration in the hip abductor muscles as a major contributor to their difficulty in maintaining and regaining balance.

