### Preliminary Studies:

We have assembled a highly qualified team of investigators with extensive expertise in performing exercise rehabilitation studies in older veterans. Seventeen older ( $75.6 \pm 4.5$ ) adults with a history of falls were recruited for a preliminary study utilizing MMBI. Subjects performed the intervention in our exercise facility 3 times/week for 16 weeks and were instructed in a home regimen to continue after completion of the center-based portion of the intervention. 16 out of 17 individuals completed all portions of the study with > 90% adherence to the protocol. Six of the 16 fell at least once during the 4 month study, and an additional six subjects reported at least 1 near fall. Four-square step times (FSST) in those who fell were significantly slower ( $12.7 \pm 6.5$  seconds) than in those who did not fall ( $5.98 \pm 2.12$  seconds), ( $p=0.009$ ). Notably, however, these individuals also had the greatest improvement with the intervention. After 16 weeks of MMBI scores on the functional gait assessment (FGA) increased by 12% and the time to complete the FSST decreased by 24%. Individuals with FSST > 10 seconds at baseline made even greater improvements of 40-50% on the FSST and FGA. Furthermore these improvements were maintained for 4 months after the completion of the exercise program. These findings warrant the application of our MMBI program to a larger study of greater duration with an active comparison group, particularly in those with a FSST > 10 seconds at baseline.

Parameter (N=16)	Baseline (mean $\pm$ SD)	16 week Post-intervention(mean $\pm$ SD)	P value
BMI (kg/m  )	26.9 $\pm$ 3.2	27.0 $\pm$ 3.2	0.40
Four-square (sec)	8.5 $\pm$ 5.3	6.1 $\pm$ 2.7	0.04
Functional gait assessment*	22.7 $\pm$ 5.9	25.5 $\pm$ 5.2	0.01
Leg extension strength	278.80 $\pm$ 110.5	299.00 $\pm$ 114.9	0.05

\*N of 8, measurement only performed on second cohort

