Aim 1: Primary Outcome Measures: Four-Square Step Test (FSST) and Functional Gait Assessment Tests (FGA). The primary outcome measures will be the change from baseline to 24 weeks in the FSST and the FGA. The FSST is a test of dynamic balance ability that assesses an individual's ability to change directions while stepping. Subjects will be timed as they step over four canes set-up in a cross on the floor. Participants will be closely guarded as they perform the test to prevent any falls. The FSST is an ideal outcome measure as it assesses the ability of an individual to dynamically maintain an upright posture while changing directions and weight shifting. It has excellent inter-rater reliability (ICC=0.99), test-retest reliability (ICC=.98), sensitivity (92%) and specificity (93%) in older adults. Older adults who take > 15 seconds to complete the task are at increased risk for multiple falls.

The FGA will also be used as a primary measure of dynamic mobility and balance and to assess fall risk. The FGA is a 10-item clinical gait test that is based on the dynamic gait index (DGI). It tests higher level dynamic gait activities that are part of daily functional mobility such as turning safely, walking at speeds required to safely cross a street, the ability to walk with head turns, gait with a narrow base of support and ambulating backwards. Each of the ten items is scored 0 to 3, with total scores ranging from 0 to 30. Scores below 22 are predictive of future falls. The FGA has excellent inter-rater reliability (ICC=.93) and predictive validity for falls. The FGA is an ideal outcome for this balance study in older veterans.

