#### Aim 1 Secondary Outcome Measures:

A clinical gait assessment as well as gait variability will be assessed using an instrumented walkway (GAITrite, CIR systems inc. Clifton, NJ). The GAITrite system is a valid and reliable system to evaluate spatial and temporal parameters of gait as well as gait variability. Gait variability is an important predictor of mobility function and fall risk in older adults, and increased gait variability predicts fall risk and mobility limitations in older adults. The GAITrite is a portable walkway mat embedded with pressure sensors that detect steps as the participant walks the length of the mat. Each participant will walk on the GAITrite 25-foot walkway at a comfortable self-selected gait speed during 4 separate trials. Outcomes will include intraindividual gait variability, as indexed by the intra-individual standard deviation for both temporal and spatial gait parameters, and walking speed determined from software provided with the GAITrite.

Questionnaires: Adults who fall may develop a fear of falling that results in curtailment of activities, and may further result in impaired mobility, balance, physical functioning and increased risk for falls. The Falls Efficacy Scale an instrument that assesses fear of falling and the activities-specific balance confidence (ABC). ABC fall scale will both be utilized to assess subjective measures of confidence in performing ambulatory activities without falling.

Lower extremity strength: A biodex dynamometer will be used to assess peak isometric hip abductor, knee extensor, and ankle plantar/dorsiflexor strength as previous work demonstrates that both knee extensor and ankle plantar flexor/dorsiflexor strength is important to mobility and fall risk. We will use standardized protocols as described by biodex.

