#### Sample Size Determination and Power Analysis

This is a pilot study with an aim towards developing estimates for effect sizes that can be used to design a larger, confirmatory randomized clinical trial. A sample size of 20 per group will allow us to detect a difference of 25% between groups for our primary outcome of the four square step test. We will enroll 40 subjects. Typical attrition rates are 25 to 30%, primarily due to time conflicts and development of non-study related medical problems. In our preliminary studies, MMBI decreased the time to complete the four square test by 24%, with even greater improvements in the frailest subjects. Time to complete the four-square test has been shown to be an excellent biomarker for fall risk.

For our second exploratory Aim the outcome will be the rate of falls and the proportion of fallers during the intervention. The sample size estimate is determined primarily by three factors; the baseline rate of falls in the study population, the duration of follow-up, and the differential impact of the two interventions on the fall rates. For example in the Lifestyle integrated Functional Exercise (LiFE) program, which embedded balance and lower limb strength training into habitual daily routines there was a statistically significant 31% reduction in fall rates (1.66 per person years) compared to controls (2.28 per person years), whereas the structured lower limb strength and balance exercises had a non-significant 19% reduction (1.90 per person years) in fall rate compared with the controls. Based on this and other literature we estimate that setting the power at 80%, alpha at 5% and with a drop-out rate of 20%, a sample size of 90 is required in each group to detect a clinically significant difference of 25% reduction in falls frequency between the two groups. Due to the budgetary limitations and duration of this VA SPIRE grant it is not feasible for us to enroll and study 180 subjects. Thus we recognize that we might not have sufficient power to see a difference in fall rate and number of falls between groups. Results from this study will be used to power a larger randomized clinical trial that will examine the effectiveness of the two interventions to reduce rate of falls and risk of falling in older veterans at high risk for falls.

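### Do two unranked primary outcomes (FSST and FGA), each tested at 0.05, need a written rule for deciding the balance hypothesis?

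*Combined protocol and SAP*

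**What the plan says.** Under Aim 1: Primary Outcome Measures the protocol states that "The primary outcome measures will be the change from baseline to 24 weeks in the FSST and the FGA". It then repeats the status of the second test: "The FGA will also be used as a primary measure of dynamic mobility and balance". Neither is ranked above the other.

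The hypothesis for Specific Aim 1 is directional and wider than these two tests: "MMBI will result in larger improvements than Tai Chi in balance, gait, lower extremity strength, and mobility fitness". The statement of the aim lists FSST and FGA together as the measures of balance, the first of the four domains.

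The section on sample size and power gives a detectable difference of 25% with 20 per group "for our primary outcome of the four square step test", in the singular, and has no matching figure for FGA. The same section opens with the purpose: "This is a pilot study with an aim towards developing estimates for effect sizes", to be used in designing a later confirmatory trial.

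The Statistical Analysis section sets one two-tailed alpha of 0.05 and compares change between groups by ANOVA, outcome by outcome. It has no testing order, alpha split or rule for combining the primaries. A separate heading, "Aim 1 Secondary Outcome Measures", covers gait, questionnaires, strength and muscle composition. The six-minute walk and adherence belong to Aim 1 but are not described under either outcome heading.

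**The concern.** Two primary outcomes, one of them used for sizing, and no success rule would be a real defect in a confirmatory trial. Three readings are open: both tests must succeed, FSST alone governs, or either suffices. The wording pulls two ways. The joint listing under balance leans towards both; the singular phrase in the sample size section leans towards FSST. If the results split, the reading could be chosen after the data are seen, and under the most permissive one the chance of a false claim would exceed 5%. The plan does state a superiority hypothesis and a significance level, so the question is fair.

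**Working it through.** **Inputs.** From the documents: two primaries; two-sided alpha 0.05, so the critical value is z = 1.96; 20 per group. The preliminary study reports FSST 8.5 to 6.1 s (N=16, p=0.04) and FGA 22.7 to 25.5 (p=0.01), the latter marked "N of 8, measurement only performed on second cohort". The documents give neither the correlation r between the two test statistics nor the power of either test. Both are assumed below, with r from 0 to 0.9.

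**The plan's own figure.** The 20 per group cannot be reproduced, because no power, SD or reference mean is stated. Under some assumptions it is near 80% power: a reference mean of 10 s makes a 25% difference 2.5 s, and with SD 2.7 s the power is 81%.

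**Error rate under each reading, no true effect on either outcome.** The two statistics are treated as bivariate normal.

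- Either suffices, either direction: 1 − P(|Z1| < 1.96 and |Z2| < 1.96). At r = 0 this is 1 − 0.95² = 0.0975.
- Either suffices, favouring MMBI: 1 − P(Z1 < 1.96 and Z2 < 1.96). At r = 0 this is 1 − 0.975² = 0.0494.
- FSST alone governs: 0.05 in either direction, 0.025 favouring MMBI.
- Both required, favouring MMBI: P(Z1 > 1.96 and Z2 > 1.96), which is 0.025² = 0.0006 at r = 0. It cannot exceed 0.025 even when one outcome has a true effect.

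| r | Either suffices, either direction | Either suffices, favouring MMBI | Both required, favouring MMBI |
|---|---|---|---|
| 0 | 0.0975 | 0.0494 | 0.0006 |
| 0.5 | 0.0907 | 0.0454 | 0.0046 |
| 0.9 | 0.0704 | 0.0352 | 0.0148 |

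Only the either-suffices reading inflates error.

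**How often the results split.** With equal power p for each test, P(exactly one significant) = 2p − 2 × P(both). At p = 0.80 and r = 0, P(both) = 0.80² = 0.64 and the split rate is 1.60 − 1.28 = 0.32.

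| r | Both significant, 80% power each | Exactly one, 80% each | Exactly one, 60% each |
|---|---|---|---|
| 0 | 0.640 | 0.320 | 0.480 |
| 0.5 | 0.687 | 0.226 | 0.322 |
| 0.9 | 0.750 | 0.100 | 0.139 |

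**What a formal rule would cost.** At 80% power each, FSST-first leaves FGA with the both-significant column, 64% to 75%. Holm gives each outcome 77% to 75%, and 0.025 each gives 71%.

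Equal power is doubtful. Taking the preliminary p-values as paired t tests:

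- FSST: SD of change = 2.4 × √16 / 2.249 = 4.27 s, a standardized change of 2.4 / 4.27 = 0.56.
- FGA: SD of change = 2.8 × √8 / 3.499 = 2.26 points, a standardized change of 2.8 / 2.26 = 1.24.

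With SD 4.27 s and 20 per group, power for a 25% FSST difference is 34%, 44% or 63% at reference means of 8.5, 10 or 12.7 s. If FSST has 44% power and FGA 80% (assumed), FSST-first gives FGA 0.44 × 0.80 = 35% at r = 0, rising to 44% at r = 0.9. FGA can never do better than the test in front of it. These inputs are small within-group samples, so they show only that the cost depends strongly on which test goes first.

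**The case for a change.** The strongest case for a change is that a split result is not rare, that the wording points in two directions, and that one sentence written in advance costs nothing in participants. The pilot label does not remove the hypothesis, the detectable difference or the 0.05 level. The protocol also expects the results to support a multisite application and MMBI programmes at other VA sites, so a statement that MMBI was better for balance would be used.

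Part of this stands. The plan does leave a combined verdict on balance undefined, and the singular reference to a primary outcome in the sample size section sits loosely beside the two named earlier. What does not follow is that the trial's conclusions are undefined. Each outcome has its own stated comparison, so a split result reads as a difference shown on one test and not on the other. No decision in the plan hangs on a single yes or no for balance. Sizing on one of two primaries does not demote the other. Nor could the two tests settle the whole hypothesis under any rule, since gait, strength and mobility fitness are also part of it.

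**Conclusion.** No change is called for. The missing element is a combining rule that a pilot can do without: both outcomes are named in advance, each has its own test, and both estimates carry into the design of the next trial. Analysts fill the gap by reporting FSST and FGA side by side with confidence intervals and describing a split as a split.

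The possible harm is a family-wise error of 7.0% to 9.75% against 5% (3.5% to 4.9% against 2.5% in favour of MMBI), for assumed correlations of 0.9 to 0. It arises only under an either-suffices reading that the plan does not state; the other two readings add no error. Choosing among FSST-first, Holm and both-required is a real trade-off. The documents do not settle it, and the obvious candidate, FSST-first, could roughly halve FGA's power under assumptions drawn partly from the preliminary data. In a confirmatory trial with the same wording the conclusion would differ.

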#### Aim 1 Secondary Outcome Measures:

A clinical gait assessment as well as gait variability will be assessed using an instrumented walkway (GAITrite, CIR systems inc. Clifton, NJ). The GAITrite system is a valid and reliable system to evaluate spatial and temporal parameters of gait as well as gait variability. Gait variability is an important predictor of mobility function and fall risk in older adults, and increased gait variability predicts fall risk and mobility limitations in older adults. The GAITrite is a portable walkway mat embedded with pressure sensors that detect steps as the participant walks the length of the mat. Each participant will walk on the GAITrite 25-foot walkway at a comfortable self-selected gait speed during 4 separate trials. Outcomes will include intraindividual gait variability, as indexed by the intra-individual standard deviation for both temporal and spatial gait parameters, and walking speed determined from software provided with the GAITrite.

Questionnaires: Adults who fall may develop a fear of falling that results in curtailment of activities, and may further result in impaired mobility, balance, physical functioning and increased risk for falls. The Falls Efficacy Scale an instrument that assesses fear of falling and the activities-specific balance confidence (ABC). ABC fall scale will both be utilized to assess subjective measures of confidence in performing ambulatory activities without falling.

Lower extremity strength: A biodex dynamometer will be used to assess peak isometric hip abductor, knee extensor, and ankle plantar/dorsiflexor strength as previous work demonstrates that both knee extensor and ankle plantar flexor/dorsiflexor strength is important to mobility and fall risk. We will use standardized protocols as described by biodex.

DXA, CT scans and Muscle Composition Assesment: Using methods developed in our previous studies total and regional % body fat, fat mass, lean tissue mass, and bone mineral content will be determined by DXA. CT scans will be performed of the abdomen, hips, and thighs using a Siemens Somatom Sensation 64 Scanner. Three CT scan slices will obtained; one at L3-L4, one at the level of the mid-thigh and the third proximal to the caput femoris. These scans will be used to quantify muscle composition and muscle attenuation for the primary hip flexors and extensors, abductors and adductors, and for the knee flexor/extensors. The cross-sectional area of the slice as well as the specific muscle group will be manually outlined as a region of interest

and muscle composition as indexed by muscle attenuation will be calculated. We hypothesize that veterans at increased fall risk will have sarcopenia and dynapenia. Training should increase muscle mass and improve muscle quality as indexed by less fat infiltration in muscle.

AIM 2 Exploratory Outcome Measure: number of falls, near falls, injuries and fall related medical visits. We will determine if there is a difference in our interventions in preventing the number of falls, near falls, injuries and fall related medical visits during the 6 month intervention. During the intervention period individuals will be instructed to call the study coordinator to report any details of all falls and near falls within 24 hours of the occurrence after enrollment into the study. The study coordinator will collect all details of the fall and near fall including the location, the activity, and hazards that may have precipitated the loss of balance, and any injuries and medical care that was required. Participants will additionally be asked at each exercise session if any falls or near falls have occurred. After the completion of the intervention all participants will be given monthly pre-stamped post cards to report any falls or near falls that may occur. The study coordinator will phone each participant monthly to follow up on any fall incidence. We have employed similar methodology in a number of studies.

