### Methods/Study Procedures:

Approach: We will enroll 56 older community dwelling veterans (age > 65 years) with a fall in the past year and evidence of balance dysfunction (FSST > 10 seconds). Our preliminary findings suggest that those with higher FSST benefit the most from MMBI. After baseline testing, individuals will be randomized to either MMBI or to a Tai Chi intervention. All participants will participate in a group exercise class in their assigned intervention for 1 hour, 3 times per week for 24 weeks. To promote camaraderie and accountability among subjects they will be enrolled in intervention cohorts of 8 to 10 subjects. At randomization subjects will be stratified first by gender then by FSST. Assessments will occur at baseline and after completion of the intervention and will include balance, mobility and fall risk, lower extremity strength, and muscle composition (total body DXA scan, hip and thigh CT scan). All participants will be followed from initial enrollment until 6 months after completion of the post-intervention testing (6 months follow up) utilizing calendar diaries, post-cards and monthly phone calls from the study coordinator to determine the number of falls, near falls, injuries and fall related medical visits.

Recruitment and Screening: A variety of methods will be used to recruit older veterans with a history of a fall in the last year, including the Baltimore GRECC subject recruitment registry, advertisements, provider referrals, community outreach, outpatient clinics and the emergency department at the VAMHCS. The use of multiple recruitment strategies will allow us to maximize our outreach to a diversity of veterans including those who have yet to seek routine care at the VA. A fall will be defined as any event that resulted in a person coming to rest unintentionally on the ground or other lower level. Prospective studies have demonstrated that older adults with a history of falls are more likely to experience subsequent falls. Exclusion criteria will include: dementia, unstable angina, poorly controlled hypertension, active substance abuse, poorly controlled diabetes, progressive neurodegenerative disease, and any other major orthopedic or health condition that would limit ability to safely exercise (see human subjects section for more

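### The plan is inconsistent on how falls are captured during the intervention; on the Aim 2 outcome text, the only scheduled prompt is tied to class attendance, so capture can differ by arm

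*Combined protocol and SAP*

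**What the plan says.** Three places in the combined protocol and SAP describe how falls are collected.

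- **Methods/Study Procedures, Approach paragraph.** "All participants will be followed from initial enrollment until 6 months after completion of the post-intervention testing", and this is done "utilizing calendar diaries, post-cards and monthly phone calls from the study coordinator". On this text, prompts that do not depend on class attendance run throughout.
- **AIM 2 Exploratory Outcome Measure paragraph.** While classes are running, the rule is that "individuals will be instructed to call the study coordinator to report any details of all falls and near falls within 24 hours". In addition, "Participants will additionally be asked at each exercise session if any falls or near falls have occurred". Post-cards come later: "After the completion of the intervention all participants will be given monthly pre-stamped post cards". The next sentence reads "The study coordinator will phone each participant monthly to follow up on any fall incidence" and states no period. Calendar diaries are not mentioned.
- **Methods/Study Procedures, paragraph after the MMBI description.** Post-cards and monthly coordinator calls are described for the six months after post-intervention testing.

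Other relevant text:

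- Sample Size Determination and Power Analysis defines the Aim 2 outcome as the fall rate and the proportion of fallers during the intervention. It gives typical attrition of 25 to 30% and says the results will be used to power a larger trial.
- Under Specific Aim 1, "H2: MMBI will have a higher adherence rate than a Tai Chi exercise program".
- Statistical Analysis promises intention-to-treat and compares the number of falls by Poisson, quasi-Poisson or negative binomial regression. It says nothing about differences in ascertainment or about how the sources are combined.

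**The concern.** A fall that nobody asks about is counted only if the participant volunteers it. On the Aim 2 outcome text, a regular attender is asked up to 3 × 24 = 72 times, while someone who has stopped attending must start every report. If more people stop in one arm, that arm's falls are under-counted, and the fitted rate ratio mixes fall risk with attendance.

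The plan itself makes this plausible. H2 predicts unequal adherence, the introduction says some Tai Chi programmes have low adherence, and the affected window is the Aim 2 outcome window. If H2 holds, more MMBI falls are found and a real benefit of MMBI is understated. If Tai Chi is better attended, the error favours MMBI. Either way, the distorted rates would pass into the design of the next trial.

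**Working it through.** **Step 1: set the texts side by side for the intervention period.**

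| Source of fall reports | Approach paragraph | Aim 2 outcome paragraph | Paragraph after MMBI description |
|---|---|---|---|
| Calendar diary | yes, from enrolment | not mentioned | not mentioned |
| Post-card | yes, from enrolment | only after the intervention | described for the six months after testing |
| Monthly coordinator call | yes, from enrolment | no period stated; follows the post-intervention sentence | described for the six months after testing |
| 24-hour call by participant | not mentioned | yes | not mentioned |
| Question in class | not mentioned | yes | not mentioned |

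Post-card timing is a direct conflict. Diaries appear in one place only. The monthly call is ambiguous. No text says which place governs.

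**Step 2: when does the class question fail?** A missed class is not a lost fall, because the next class can pick it up. With 70% attendance (assumed) and absences scattered at random, the chance of missing three given consecutive classes is 0.3³ = 0.027, about 3%. The problem therefore comes from prolonged absence or withdrawal.

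**Step 3: effect on the rate ratio.** The plan gives no capture figures, so all inputs here are assumptions:

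- s = share of falls reported by the participant's own call;
- u = share of falls in time with no class prompt to follow (M = MMBI, T = Tai Chi);
- m = share of otherwise missed falls recovered by diaries, post-cards or monthly calls.

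Capture = 1 − (1 − s) × u × (1 − m).
Observed rate ratio = true rate ratio × capture(M) / capture(T).

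Take u(M) = 0.10, suggested by the pilot's adherence above 90%, a true ratio of 0.75 (the 25% reduction in the sample size section) and m = 0 (Aim 2 text only). Example with s = 0.5 and u(T) = 0.20: capture is 1 − 0.5 × 0.10 = 0.95 against 1 − 0.5 × 0.20 = 0.90. The ratio is 1.056 and the observed value is 0.75 × 1.056 = 0.79.

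| u(T) | s = 0.3 | s = 0.5 | s = 0.7 | s = 0.9 |
|---|---|---|---|---|
| 0.10 | 0.75 | 0.75 | 0.75 | 0.75 |
| 0.20 | 0.81 | 0.79 | 0.77 | 0.76 |
| 0.30 | 0.88 | 0.84 | 0.80 | 0.77 |
| 0.50 | 1.07 | 0.95 | 0.86 | 0.78 |

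A rough anchor for u: if 30% withdraw evenly over the period, about 0.30 / 2 = 0.15 of person-time is unprompted, which is the average of 0.10 and 0.20. The last row averages 0.30, which would need all 30% to stop at the outset. The 0.20 row is thus nearest to the plan's attrition figure, and the last row is an extreme. The split between arms is assumed throughout.

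**Step 4: the Approach methods also running.** With u(T) = 0.30 and m = 0.8, s = 0.3 gives (1 − 0.7 × 0.10 × 0.2) / (1 − 0.7 × 0.30 × 0.2) = 0.986 / 0.958 = 1.029, so 0.75 is observed as 0.77. With s = 0.7 it is 0.76. Most of the bias disappears.

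**Step 5: compare with sampling error.** Take 20 per arm, half a year, and the cited trial's control rate of 2.28 per person-year as an illustration. Expected falls are 20 × 0.5 × 2.28 = 22.8 and 22.8 × 0.75 = 17.1. The standard error of the log ratio is √(1/22.8 + 1/17.1) = 0.32, so the 95% limits multiply or divide the ratio by exp(1.96 × 0.32), about 1.9.

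**The case against.** The strongest reply is that the Approach paragraph already promises uniform follow-up of all participants from enrolment. If it governs, people who leave class are still prompted and Step 4 applies. The Aim 2 paragraph may be an incomplete account: its class question is described as additional, and its monthly call has no stated period. This stands as a limit on the claim. It does not remove the conflict over post-cards, and the other two paragraphs lean towards post-intervention use.

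Three stronger readings are tempting, and the documents do not support them.

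- **That the fall comparison is biased as planned.** Bias needs unequal prolonged absence, incomplete self-report and no other prompts in the period. H2 is a hypothesis, and the attrition figure is not split by arm.
- **That people who stop attending are never prompted.** That is so only if the Approach paragraph is set aside.
- **That the change of method after the intervention confounds the comparison.** The planned analysis is between arms, and a method common to both arms does not by itself confound a contrast within one period.

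It is also fair to say that Aim 2 is exploratory and admittedly underpowered, that sampling error is far larger than the illustrated bias, and that the error predicted under H2 runs against the trial's own hypothesis. These points lower the stakes. They do not justify leaving the capture method unsettled, since a systematic error in the rates would carry into the next trial's design.

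**Conclusion.** The concern holds as a conflict between passages with a conditional risk of bias. The plan does not settle how falls are captured in the window that defines the Aim 2 outcome. If the Aim 2 paragraph is followed as written, capture can differ between arms through prolonged absence or withdrawal. If H2 is right, the rate ratio is then biased against MMBI.

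The size cannot be determined from the documents. Across the assumed grid the multiplier on the rate ratio runs from 1.00 to 1.43. In the row nearest the plan's attrition figure it is 1.01 to 1.08. It is 1.00 when absence is equal or self-report is complete. The change should be made before falls are collected, but it does not threaten the primary outcomes.

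**What to change.** Reconcile the three places by amending the Aim 2 outcome paragraph, and align the other two with it:

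1. A falls calendar or post-card plus a scripted monthly coordinator call runs from randomisation to the end of follow-up, for every randomised participant, including those who miss or stop classes.
2. The 24-hour call and the in-class question stay as additional sources, and falls from all sources are counted. Counting only falls confirmed by calendar or monthly call would discard valid falls reported by the 24-hour call, which does not depend on attendance.
3. The source of each fall is recorded, and a sensitivity analysis excludes falls found only by the in-class question.

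The cost is about six extra calls and post-cards per participant relative to the Aim 2 paragraph, which the Approach paragraph already plans. Falls in people who decline all further contact will still be missing.
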